Aim 1: Use rtfMRI-NF and motor imagery to train CA participants to improve motor accuracy.

- Aim 1.1: Train CA participants (N=30) to engage neural regions during motor imagery that are associated with overt finger tapping at slow (1 Hz) and fast (4 Hz) speeds.
- *Aim 1.2:* Correlate motor imagery skill (i.e., slider bar distance from target) with overt tapping performance.

• *Aim 1.3:* Evaluate the relations between overt tapping accuracy and neurological symptoms as well as motor imagery skill with offline assessments of motor imagery ability.

Aim 1 will use rtfMRI-NF during motor imagery to train CA participants to improve motor accuracy. Thirty CA participants will receive NF during motor imagery in an experiment in which we hypothesize that 1) CA participants will be able to control a NF interface; 2) imagery skill will be positively correlated to improvements in overt tapping accuracy; and 3) overt tapping accuracy will correlate with neurological signs, whereas motor imagery skill will correlate with assessed motor imagery ability.

Aim 2: Translate rtfMRI-NF learning into at-home therapy strategies for continued training.

- Aim 2.1: Examine whether motor imagery strategies from rtfMRI-NF training translate into successful at-home therapy training
- *Aim 2.2:* Compare motor imagery performance during rtfMRI NF with at-home motor imagery benefits.

Aim 2 will translate rtfMRI-NF learning into at-home therapy strategies for three weeks of continued training in which we hypothesize that 1) continued practice with imagery strategies will lead to additional improvements in motor timing and precision, and 2) performance during rtfMRI-NF training will positively correlate with at-home motor imagery performance.

Exploratory

Aim 3: Design next-generation approaches to rtfMRI-NF. The data from Aim 1 will be analyzed to optimize the future rtfMRI experiments in the CA population. We will examine whether the NF session can be streamlined to deliver more accurate NF in shorter sessions. To enable future studies to operate within an experimental medicine frame work we will examine three major questions. Aim 3.1 Are there group differences in CA versus healthy controls? Aim 3.2 Are healthy models of motor imagery viable for CA participant NF? Aim 3.3 Can the NF session be streamlined to deliver more accurate NF in more efficient sessions?

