function following injury can be regained through neural reorganization, but motor execution is not always possible or safe. Numerous clinical studies have indicated that motor imagery improves motor performance, especially when used as an adjuvant treatment with physical practice [11]. Yet, due to its very nature, motor imagery cannot be directly observed. This makes it difficult to assist and evaluate a patient's motor imagery process. Brain activity associated with motor imagery is, however, observable through neuroimaging. Moreover, with the recent development of technologies like real-time functional magnetic resonance imaging neurofeedback (rtfMRI-NF), motor imagery "behavior" can be displayed to both the patient and the clinician. For example, NF can be presented as a slider bar to indicate the degree to which a motor imagery strategy is working. Moreover, rtfMRI-NF may provide a quantifiable, objective marker of motor imagery performance, since the degree of NF control is proportional to the success of imagery to engage relevant brain regions.

We will combine rtfMRI-NF with imagery to facilitate motor network ("exercise") to improve function in CA. We will use support vector machines (SVMs) to extract motor imagery patterns and perform rtfMRI-NF as pioneered by LaConte [12, 13] (Figure 4). The SVM is first trained on an individual's fMRI patterns while performing a simple motor task (e.g., finger tapping in sync with a flashing visual cue). SVM is then used to provide neurofeedback during a subsequent task (e.g., motor imagery of finger tapping). Information about the brain's activity during motor imagery is relayed back to the person in the form of an "error signal" (i.e., distance from a target on a slider bar). Participants can use this neurofeedback to learn strategies for motor imagery that implicitly steer their brain towards optimal patterns of neural activity. As the participant changes their mental strategy, neurofeedback indicates whether the new strategy is working.

RtfMRI-NF is safe, can be performed even when physical movement is severely impaired, and targets the underlying neural responses directly rather than the

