downstream physical signs. Although alternative cheaper and more portable imaging modalities may ultimately be adapted if this line of research garners success, fMRI is currently the best general purpose, whole-brain, non-invasive technology available for human research. Thus, the benefit of rtfMRI is that while this application optimally explores motor imagery's therapeutic potential, it simultaneously addresses a critical need to better delineate motor control and imagery circuitry in CA. Since rtfMRI-NF is a relatively new technology [14], research is only beginning to explore its clinical uses. Most clinical studies to date have been conducted in psychiatric populations [15-26] which have reported symptom reductions in association with NF modulation of brain networks.

motor imagery [2].

Only a handful of rtfMRI-NF studies have been conducted in neurologic conditions. In three stroke studies, participants (N=15 total) were able to modulate brain networks to improve motor and visuomotor function [27-30]. In three studies of Parkinson's disease (PD), [31-33] results have been encouraging. Tinaz et al. (2018) found that eight PD patients were able to modulate connectivity between the insula and prefrontal cortex, which was the *a priori* target of interest; however, the modulation had no effect on motor function. A slightly larger PD study by Subramanian et al. (2016) compared rtfMRI-NF training plus at-home motor training (N=13) to at-home motor training only (N=13). The rtfMRI-NF a priori region of interest was the supplementary motor area (SMA) based on earlier findings that NF training to modulate the SMA correlated with reduction in PD motor symptoms (N=10) [31]. They replicated successful modulation of the SMA using rtfMRI-NF, and motor function improved by 20%. They reported trend-level correlations between NF success and motor function improvements. Moreover, improvements in the rtfMRI-NF group were 2-fold greater than in the exercise-only group (who did not show clinically relevant change), yet this group difference did not reach statistical significance. The authors suggested that studies with larger sample sizes are warranted. It is also notable that PD participants were guided to engage their SMA, even though additional regions were determined to upregulate with NF training, including the frontal lobe, anterior cingulate, basal ganglia, and cerebellum. Thus, our proposed agnostic, whole-brain classifier approach may be advantageous.

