When the neuropsychological testing portion of the visit is completed, they will then be trained on a cognitive task that will be administered inside the MRI. If they are a woman of childbearing age, they will be given a urine drug pregnancy test. If the pregnancy test is positive, they will be removed from the study and PHI and any data collected thus far will be destroyed. After training and pregnancy test if needed, they will be escorted to the F.M. Kirby Research Center across the street, which houses the MRI scanner. Participants will be asked to arrive 1 hour before the MRI scan is scheduled to begin. Total time spent in the scanner will be approximately < 1 hour, and

Task	Approximate Time (minutes)
Training on cognitive test (outside the scanner beforehand)	10
MPRAGE	6
Overt tapping	12
Motor imagery	12
Overt tapping	12

we will reserve 1 full hour to allow time to get in and out of the scanner for this movement disordered population.

Participants will perform an overt tapping test as a baseline measure of online task performance. Therapy begins the next day and lasts for 21 days (participants complete at least 5 days per week to accommodate scheduling conflicts). A final measure of overt tapping will be performed the day after therapy ends. Participants will be randomly assigned to one of three training conditions. Group 1, imagery only; Group 2, overt tapping only; and Group 3, imagery plus overt tapping. During imagery, participants will view the task while imagining that they are finger tapping in time with the flashing cursor, using the imagery strategies identified during their rtfMRI-NF session. During overt tapping, participants will finger tap in time with the flashing cue.

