Participants will be instructed to find a quiet room with minimal distractions and remain in a comfortable seated position with their hands resting on the keyboard. All tests include blocks of trials in which either 1 or 4 Hz cues are presented. In the baseline and final measures, a session will consist of one 4-minute test comprised of 12 blocks; each frequency will be presented six times. In the 3-week therapy component, a session will consist of two 2-minute tests comprised of six blocks each; each frequency will be presented three times per block. In all sessions, frequency blocks will be pseudorandomized such that the first block will always be the 1 Hz frequency, and the same frequency will be presented in no more than three consecutive blocks. All blocks begin with 5 seconds of rest, followed by 15 seconds of the flashing cue. After completion of their experience for the day (e.g, vividness of imagery, perceived tapping precision, etc.).

	BASELINE M	EASURE	3 WEEKS OF AT-HOME THERAPY CONDITIONS				FINAL MEASURE	
	Overt tapping (4 min)	Daily log (3 min)	Imagery (4 min)	Overt tapping (4 min)	Imagery + overt tapping (2 + 2 min)	Daily log (3 min)	Overt tapping (4 min)	Daily log (3 min)
Group 1 (n=10)	X	X	X			X	X	X
Group 2 (n=10)	X	X		X		X	X	X
Group 3 (n=10)	X	X			X	X	X	X

b. Study duration and number of study visits required of research participants.

Each participant will have 1 in-person study visit (day 1) that will take about 3-4 hours. Days 2-23 of the study will consist of at-home therapy 5x weekly that may take up to 10 minutes to complete. At-home therapy includes a baseline online measure and log (7 minutes), group designated tasks (See table below) and log (7 minutes), and a final online measure and log (7 minutes). The total duration of the study is 2 years of data collection and analyses (allowing up to 3 additional years of data analyses).

General Study Protocol					
Event	Tasks Completed	Duration			
Screening	Clinical appropriateness	15-20 minutes			
(phone)					
	Consent*, pre-MRI pregnancy test	25-30 minutes			
Screening					
(In-person)					
In-person	Task orientation	10-15 minutes			
visit	MRI: Anatomical scan and rtfMRI-NF	1 hour (42 min			
		active MRI)			
	Questionnaires*, assessments*, neurological exam, at-home	2 hours			
	instructions				
At-home	Baseline online measure & log	7 minutes			
therapy	Training according to group assignment: Group 1 = motor	7 minutes per			

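### The imagery score comes from a whole-brain classifier trained on tapping to a flashing cue, and no described analysis separates the response to the cue from motor imagery

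*Combined protocol and SAP*

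**What the plan says.** Section 3 (Background) describes an SVM trained on an individual's "fMRI patterns while performing a simple motor task (e.g., finger tapping in sync with a flashing visual cue". It continues: "SVM is then used to provide neurofeedback during a subsequent task (e.g., motor imagery of finger tapping". On the choice of brain regions, the same section says "our proposed agnostic, whole-brain classifier approach may be advantageous". The text names neither the classes the SVM separates nor any voxel mask.

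Aim 1.1 in Section 2 is to train participants "to engage neural regions during motor imagery that are associated with overt finger tapping at slow (1 Hz) and fast (4 Hz) speeds". Aim 1.2 defines imagery skill as slider distance from target, and Section 3 gives the interpretation: "the degree of NF control is proportional to the success of imagery to engage relevant brain regions".

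On what is seen during imagery, Section 4a says that "participants will view the task while imagining that they are finger tapping in time with the flashing cursor". This describes the three-week at-home training, as the reference back to strategies found in the scanner session shows. The timing statement, "All blocks begin with 5 seconds of rest, followed by 15 seconds of the flashing cue", also belongs to the at-home sessions. For the scanner imagery run, the text gives 12 minutes (Section 4a) and slider-bar feedback (Section 3). It does not say whether the flashing cue is displayed.

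The only in-scanner check described is EMG for finger movement (Section 8a), which a participant may decline (Section 8b).

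**The concern.** If cue and movement always change together in training, the trained pattern may include the response to the cue. Should the cue then appear during imagery, the slider would move partly because the participant is looking at the screen. Control of the slider would no longer show imagery by itself. Differences between participants in visual response would add noise or bias to the imagery-score correlations. Participants could also be rewarded for strategies that are not motor, and then practise them at home for three weeks. EMG cannot detect this, because it shows unwanted movement and not the absence of imagery. No passive-viewing run, sham feedback or check of classifier weights is described.

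**Working it through.** The plan gives no classifier accuracy or effect size, so there is no figure to reproduce. The check has two parts.

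**What the text establishes**

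1. *Training cue.* Section 3 gives the flashing cue only as an example. However, Section 7c says that the tapping task of the first two pilot studies is the one proposed in Aim 1, and Section 3 describes that task as tapping to a cue flashing at 1, 2, 3 or 4 Hz. The cue in training is therefore well supported.
2. *Class labels.* If the classes are tap versus rest, cue on/off follows the label (assuming the scanner blocks share the at-home rest-then-cue structure). If they are 1 Hz versus 4 Hz, cue rate follows the label. Under either labelling, visual input is aligned with movement.
3. *Cue during scanner imagery.* Not stated. In favour: imagery is at 1 and 4 Hz, the flashing cue is the only pacing signal described, and at-home imagery reuses scanner strategies. This is an inference.

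**How large the effect could be if the cue is shown**

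Assumptions, none from the documents: an optimal linear classifier and independent motor and visual features, with class separations d'm (motor) and d'v (visual). Let D = √(d'v² + d'm²). The participant watches the cue and imagines nothing.

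- *Symmetric labelling or re-set threshold:* accuracy = Φ(½ · d'v²/D).
- *Tap versus rest with the trained threshold:* cue-on volumes are called tap with probability Φ((d'v² − d'm²)/(2D)), and rest volumes are correct with probability Φ(D/2). Balanced accuracy is the mean of the two.

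Example, d'm = 2 and d'v = 1: D = √5 = 2.236. The first formula gives Φ(0.224) = 58.8%. The second gives Φ(−0.671) = 25% and Φ(1.118) = 87%, mean 56%.

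| d'm | d'v | Re-set threshold | Called tap, trained threshold | Balanced accuracy, trained threshold |
|---|---|---|---|---|
| 2 | 1 | 58.8% | 25% | 56.0% |
| 2 | 2 | 76.0% | 50% | 71.1% |
| 2 | 3 | 89.4% | 76% | 86.0% |
| 1 | 1 | 63.8% | 50% | 63.0% |
| 1 | 2 | 81.4% | 75% | 80.9% |
| 1 | 3 | 92.3% | 90% | 92.0% |

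For a weak cue effect, d'v = 0.25 to 0.5, the first formula gives only 51% to 55%. Chance is 50%.

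A simulation with a linear SVM gives the same direction. It used 50 motor, 50 visual and 100 noise features, 180 volumes, 60 repetitions and symmetric labels. The assumed class difference per voxel was 0.5 SD for tapping and 0.25 SD for imagery.

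| Cue effect relative to motor effect | Watching only, all features | Imagery with cue, all features | Imagery without cue, all features | Watching only, visual features removed | Imagery with cue, visual features removed |
|---|---|---|---|---|---|
| 0 | 50.4% | 73.2% | 73.1% | 50.7% | 73.3% |
| 0.25 | 52.7% | 75.7% | 73.5% | 50.4% | 74.1% |
| 0.5 | 61.3% | 81.4% | 73.2% | 49.7% | 74.5% |
| 1.0 | 85.4% | 93.4% | 69.6% | 51.0% | 74.4% |

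The return to chance without visual features follows from the set-up, which placed the cue signal in those features only. Real motor regions may respond to a rhythmic cue, so a motor mask reduces the ambiguity without proving it away.

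**The case against.** The strongest reply is that the link to the scanner is missing. The sentences that put the cue on screen during imagery concern home sessions, where there is no scanner, SVM or slider score. If no cue is shown in the scanner imagery run, a participant cannot earn the score by watching it. This stands. A reader might infer from Section 4a that the scanner score is contaminated, but the documents do not support that as fact.

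The class labels and any mask are also unstated in the text, and could be given in Figure 4 or in the method references cited in Section 3, which were not available. This stands as well, and is a reason to ask for both.

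The percentages rest wholly on assumed separations. Under tap versus rest with the trained threshold, a watcher is mostly classified as resting whenever d'v is below d'm. It would be wrong to read 59% to 92% as an estimate for this trial.

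The plan has partial safeguards. Secondary outcome 2 uses regional activity. Correlation with the KVIQ is a convergent check that a cue-driven score should tend to fail. Section 7c reports that motor-region activity during imagery tracked tapping improvement in healthy adults. Offline reanalysis is foreseen in Aim 3. None of these isolates the visual contribution to the slider score.

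Finally, whole-brain input is a reasoned choice: Section 3 notes that regions beyond a single target were upregulated in earlier work in Parkinson's disease. That is a fair argument against masking the real-time feedback. It does not weigh against an additional offline score.

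**Conclusion.** The concern holds in conditional form. Cue and movement are aligned in the training data of a classifier described as whole-brain, and no described analysis separates them when slider distance is read as imagery skill. Whether this inflates the score depends on whether the cue is shown during scanner imagery and how much class information it carries. The plausible size is therefore nil to large, and the documents give nothing to narrow it.

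The affected analyses are Aim 1 hypothesis 1 (control of the interface), Aims 1.2, 1.3 and 2.2, and secondary outcomes 1 and 3 in Section 7b, taking imagery accuracy there to be the slider-based score. A reader might extend the doubt to the trial's main result, but the documents do not support that: both primary outcomes in Section 7a are overt tapping accuracy, and the correlation in Section 7b item 2 uses regional activity, so neither directly depends on the score.

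This is a worthwhile, inexpensive improvement to the mechanistic conclusions, not a defect in the primary analysis.

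**What to change.** 1. State the SVM classes, any voxel mask, and whether the flashing cue is displayed during scanner imagery.
2. Keep the real-time feedback whole-brain.
3. Pre-specify an offline re-computation of each participant's imagery score, on the same data, from an SVM limited to a motor mask: M1, premotor cortex, SMA and cerebellar motor regions, from the atlases already cited in Section 7c.
4. Report Aim 1 hypothesis 1 and all imagery-score correlations with this score beside the slider score. Claim imagery control only if the motor-mask score supports it.
5. Report a visual-cortex-only classifier as negative control. A result above chance shows that visual areas carry class information during imagery. It does not show that imagery was absent, so it should be read together with the motor-mask score.

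The cost is some added offline analysis and no new data. The motor-mask score leaves out information from non-motor regions, which is why it is reported alongside the slider score.

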Figure 1. Finger tapping speed and accuracy in CA. Top row: The CA group showed impaired accuracy at 1, 2 (trend), 3, and 4 Hz. Bottom row: The CA group tapped too fast at 1 Hz and too slow at 4 Hz. Yellow= group means. Error bars denote standard error [1].

slider bar that moved to the left as participants tapped too slow and to the right as they tapped too fast. We anticipated that CA participants would be able to use the external cues of the slider bar to correct tapping errors in real time, rather than rely on internal models of timing intervals.

Tapping accuracy, measured by root-mean-squared error (RSME) relative to target, was impaired at all tapping rates. Relative to controls, the CA group's tapping speed was too slow at 4 Hz, and too fast at 1 Hz. Tapping too fast at 1 Hz suggest an inability to control movements to slow down. Over/undershoot corrections in finger movements likely averaged out and masked group differences in speed 2 and 3 Hz, but were revealed in the slow (1 Hz) and fast (4 Hz) conditions. In CA, higher symptom severity, as measured by the International Cooperative Rating Scale (ICARS), was associated with slower tapping and greater error magnitude. Together, these results suggested that accuracy and speed are dissociable measures, with accuracy being the more sensitive measure of motor impairment in CA. Moreover, the 1 and 4 Hz conditions represented especially interesting tapping rates to study given the contrasting behaviors at each speed. We conducted a follow-up study to explore whether the feedback from the slider bar improved or degraded tapping behavior. We found that both groups slowed their tapping speed in the absence of continuous feedback, but the CA group's tapping accuracy deficits persisted. Based on the differences between 1 and 4 Hz, we speculate that 4 Hz may be close to the tapping limits of CA participants, but 1 Hz represents a trainable target for improving motor timing from paced visual feedback. Thus, this application's focus on 1 and 4 Hz builds on a foundation of preliminary data and aims to tease apart deficits in production from those of top-down feedback processing. We conducted an fMRI pilot study to identify neural activity patterns associated with right-

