2) At-home overt tapping accuracy improvements will be analyzed by comparing the mean accuracy on overt tapping between baseline and final measures at home (pre- and post- 3-week at-home therapy training) to compute a delta measure that will indicate magnitude of accuracy improvement at each frequency (1 and 4 Hz). This will be analyzed using paired t-tests within frequency conditions. As a follow-up analysis of improvement during the 3-week therapy (for training Groups 2 and 3 who perform daily overt tapping exercises), the mean accuracy of overt tapping at both frequencies will be measured for each session and compared using repeated measures ANOVAs and post-hoc t-tests as appropriate.

b. Secondary outcome variables.

1) The relation between imagery accuracy and tapping accuracy with supplemental assessments of imagery and motor symptoms will be analyzed using non-parametric correlation tests, such as Spearman's rank-order correlation coefficient test, because of the ordinal values in the KVIQ and ICARS assessments. Mean imagery accuracy and tapping accuracy scores from the final MRI assessment will be compared separately to the KVIA an ICARS.

2) The relation between brain activity during imagery NF and overt tapping improvements will be analyzed using Pearson correlations between the mean of region of interest activity (minus rest) during NF training and the RSME delta scores.

3) The influence of ancillary measures on overt tapping and motor imagery accuracy will be analyzed using non-parametric correlation tests (e.g., Spearman's rank) because of the ordinal values in the HAM-A, HAM-D, CCAS, and WRAT assessments. Mean imagery accuracy and tapping accuracy scores from the final MRI assessment will be compared separately to each of the assessments.

c. Statistical plan including sample size justification and interim data analysis.

We plan to enroll 30 participants in this study. The sample size was determined through a power analyses using G*Power 3.1.9.2 software [40]. Because motor imagery, with or without rtfMRI-NF, has never been used as a treatment approach for people with cerebellar ataxia (CA), as proposed here, our power analyses are extrapolated from information we have obtained that in three prior studies that support the premise and feasibility of Aim 1, which is to use rtfMRI-NF and motor imagery to train CA participants to improve motor accuracy.

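### Block 1 of the home baseline and final tests is always a scored 1 Hz block, so any fall in start-up error between the two tests loads mainly on the 1 Hz change score

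*Combined protocol and SAP*

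**What the plan says.** Section 4a sets the order of the home task for all sessions: the order is pseudorandomised, but "the first block will always be the 1 Hz frequency", with the further limit that "the same frequency will be presented in no more than three consecutive blocks". For the baseline and final measures, "a session will consist of one 4-minute test comprised of 12 blocks; each frequency will be presented six times". On block timing: "All blocks begin with 5 seconds of rest, followed by 15 seconds of the flashing cue". For the three-week therapy phase, "a session will consist of two 2-minute tests comprised of six blocks each". The protocol describes no warm-up block, discarded first block or counterbalancing of the first frequency, and gives no reason for the rule.

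Section 7a, item 2, makes the change in mean overt tapping accuracy from home baseline to home final measure a primary outcome, computed separately at 1 and 4 Hz: "This will be analyzed using paired t-tests within frequency conditions". It states no alpha or sidedness for this test. Section 4e gives N/A for a non-treatment group.

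Before the home phase, the table in section 4a lists 10 minutes of task training, two 12-minute overt tapping runs and 12 minutes of imagery at the scan visit. Section 4b places the home phase, including its baseline measure, after that visit.

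**The concern.** The first seconds of a test can carry error that has little to do with timing skill, such as settling in and catching the cue. With a fixed first frequency, that error always enters the score of the same frequency.

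A stable start-up error cancels in a before-after difference; one that shrinks does not. The baseline is the first use of the online test on the participant's own computer. The final test follows three weeks of sessions on at least 5 days a week, so at least 15 sessions. Familiarity with that set-up could reduce start-up error without better motor timing, and the reduction would count as a 1 Hz improvement on a primary outcome. All three groups use the task during therapy, so there is no untrained group to reveal the artefact.

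The direction matters for interpretation. Section 3 speculates that 4 Hz may be near participants' limits while "1 Hz represents a trainable target for improving motor timing from paced visual feedback". A gain larger at 1 Hz than at 4 Hz would fit that expectation even if part of it came from block order.

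**Working it through.** **Inputs from the protocol.** 12 blocks per baseline or final test, 6 per frequency; 5 s rest + 15 s cue per block; block 1 fixed at 1 Hz; at most three consecutive blocks of one frequency (all section 4a). n = 30 (section 7c). Paired t-test within frequency (section 7a).

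**Inputs assumed.** x, the fall in block-1 start-up error from baseline to final as a share of mean error: 10-50%. SD of the change score: 20-30% of mean error. Two-sided alpha .05. All 30 participants pooled. Allowed block orders equally likely.

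**1. The plan's own figure.** 12 × (5 + 15) s = 240 s = 4 minutes; 6 × 20 s = 120 s = 2 minutes. Both stated test lengths reproduce.

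**2. Weight of block 1.** 1/6 = 16.7% of the 1 Hz mean; 0 of the 4 Hz mean.

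**3. Bias.** Let s0 and s1 be the block-1 excess error at baseline and final. The 1 Hz change is shifted by (s0 − s1)/6 = x/6. If s0 = s1, the shift is zero.

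**4. False-positive rate with no true gain.** Standardised shift d = (x/6)/SD; noncentral t with df = 29 and noncentrality d√30.

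| x | x/6 | d (SD 30% to 20%) | Rejection rate |
|---|---|---|---|
| 0 | 0 | 0 | 5% |
| 10% | 1.7% | 0.056 to 0.083 | 6-7% |
| 20% | 3.3% | 0.111 to 0.167 | 9-14% |
| 30% | 5.0% | 0.167 to 0.250 | 14-26% |
| 50% | 8.3% | 0.278 to 0.417 | 31-60% |

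Within a single group of 10, x = 30% gives 7.6% (SD 30%) to 10.9% (SD 20%).

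**5. Error lasting beyond block 1.** Listing every 12-block order that meets the rules gives 308. Block 2 is 4 Hz in 59.7% of them and block 3 in 57.5%. Mean block position is 6.04 at 1 Hz and 6.96 at 4 Hz. If the excess decays as 1, 0.5, 0.25 over blocks 1-3 (assumed):

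- 1 Hz: (1 + 0.403 × 0.5 + 0.425 × 0.25)/6 = 0.218 of the block-1 excess
- 4 Hz: (0.597 × 0.5 + 0.575 × 0.25)/6 = 0.074

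The loading is then about 3 to 1, not on 1 Hz alone.

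**6. Effect of a remedy.** Leaving block 1 unscored takes the block-1 bias from x/6 to 0 and, for error confined to block 1, returns the rate to 5%. Under the decay example, dropping block 1 leaves (0.403 × 0.5 + 0.425 × 0.25)/5 = 0.062 at 1 Hz against 0.074 at 4 Hz, roughly even. Counterbalancing the first frequency instead gives x/12 at each frequency: the artefact is shared, not removed.

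**The case against.** The strongest reply is that start-up error may be small and largely stable. Participants come to the home baseline with 10 minutes of training and 24 minutes of scanner tapping behind them, and section 4b lists task orientation and home instructions at the visit. They sit with hands already on the keyboard, and each block opens with 5 seconds of rest, so launching the test and finding the key can happen before any scored tap. The final test starts the same way. Group 1 makes no home taps between baseline and final, so a complete loss of tapping start-up error there is doubtful; if a 30% excess disappeared only in Groups 2 and 3, the average x would be 30% × 20/30 = 20%, and the rate 9-14%. All of this stands. It limits the likely size of the bias but does not remove the mechanism.

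A reader might infer several stronger points that the documents do not support:

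- That the baseline is unpractised. Only the online home set-up is new.
- That 4 Hz is untouched. This holds only if start-up error ends with block 1.
- That two of six 1 Hz blocks are affected in each daily session. Group 1 does no daily tapping, and Group 3 taps in only one 2-minute test. The rule is written per session, so the first frequency of a second test is not stated. Daily tapping is in any case a follow-up analysis.
- That a planned comparison of 1 Hz with 4 Hz is compromised. No such contrast is specified, the hypotheses in section 2 do not mention one, and section 3 only speculates about the difference.

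It is also fair that the study is presented as feasibility and pilot work, and that general practice gains over all 12 blocks are a separate issue that this point does not address.

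**Conclusion.** The point holds as a limited, avoidable source of bias in one primary outcome. The rule and the scoring together make block 1 one sixth of the 1 Hz mean and none of the 4 Hz mean, with no stated safeguard. Only the reduction in start-up error between the two tests biases the result, by x/6 towards a 1 Hz gain.

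Whether that matters depends on x, which the documents do not give. At x = 10% the false-positive rate hardly leaves 5%; at 30% or more it would be serious. These rates rest on the assumed SD of 20-30%, two-sided .05, pooling of all 30 participants and x being the average reduction across them. The documents do not support a claim that the 1 Hz result will be materially biased. They do support a low-cost change.

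**What to change.** Start each home baseline and final test with one unscored 20-second lead-in block, then randomise the 12 scored blocks with no fixed first frequency, keeping the limit of three consecutive blocks. For consistency, do the same in each daily tapping test. State the scoring rule in section 7a. Cost: a small change to the task program and 20 s per test.

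If the program is already fixed, specify before analysis that block 1 is dropped from the 1 Hz mean at both baseline and final. The 1 Hz mean then uses 5 rather than 6 blocks, and its within-session standard error rises by at most about 10% (√(6/5) = 1.095).

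Neither option deals with general practice effects, which affect both frequencies.
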